For Aim 2, [name] will provide motivational interviewing training to HIV Alliance staff and volunteers to facilitate their delivery of Connect2Test with clients. [name] will provide opportunities for practice and feedback.

3. Training and Oversight

Co-investigators and research assistants will perform research activities within the scope of their training.

Training for research assistants and HIVA testing facilitators who collect data from participants will be provided by the research team. Training will include how to sanitize devices used for data collection, relevant human subjects training, and standardized processes and procedures for data collection.

HIV Alliance staff will participate in an alternative human subjects training plan for these individuals. Specifically, a researcher with human subjects training will provide human subjects training during the training already being conducted by the research team. All HIV Alliance staff will be added to the research plan and will complete Individual Investigator Agreements (IIA)s if they are not affiliated with the UO. Alternative training procedure and training dates will be documented in the research records.

Statistical Analysis Plan

Official Title: Motivational Enhancement to Augment Contingency Management for SARS-CoV-2 Testing and Vaccination Utilization Among Syringe Exchange Clients

NCT number: NCT05534061

Document Date: July 26, 2022

Statistical Analysis Plan

Study Title: Creating a Sustainable Infrastructure for SARS-COV-2 Testing at Syringe Exchange Programs

Protocol Number: 11162020.013

Preliminary analyses included a description of the sample and extent of missing data and tests of baseline equivalency of randomized groups. Study participants received the intervention across nine sites resulting in a multilevel data structure. We used multilevel logistic regression estimated with the generalized linear model using the adaptive quadrature quasi-likelihood estimator to compare rates of COVID-19 testing and vaccination administered on the same day of the intervention and anytime during the 9-month follow-up period. A Bernoulli distribution and logit link function were specified, and odds ratios and 95% confidence intervals reported to facilitate interpretation. First, a null model was specified to estimate the variability between sites and within individuals followed by the full model that included the study randomized condition as the predictor (coded 1 = CM + Connect2Test, 0 = CM).

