2a: Adapt Connect2Test to 1) address the continued necessity of SARS-CoV-2 testing in the context of vaccine accessibility and vaccine hesitancy, 2) enhance vaccine uptake, and 3) enhance acceptability, appropriateness, and feasibility of the intervention based on lessons learned during Phase I.

2b: Conduct a 2-arm randomized control trial to evaluate the comparative effectiveness of CM alone (arm 1) versus CM plus the adapted Connect2Test intervention (arm 2) on SARS-CoV-2 testing and COVID-19 vaccination uptake.

Aim 3: Evaluate the implementation of CM and Connect2Test including: 1) an assessment of reach, acceptability, appropriateness, feasibility, fidelity, penetration, and sustainability, and 2) a cost-effectiveness analysis of CM versus CM + Connect2Test.

C. Methods, Materials and Analysis

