Overall Study Design: This study involves development and implementation of a COVID-19 testing and vaccination program embedded in HIV Alliance's (HIVA) Syringe Service Programs (SSP) at 10 sites across Oregon (Aim 1). We will evaluate testing and vaccination utilization rates as our outcome for Aim 1. Across all sites, for Aim 1, we will administer approximately 150 tests per week for a total of 15,600 tests over the study period. We will also administer a total of 1,200 vaccines during the study period. Some of these individuals will be repeat testers and vaccinators. For Aim 1, we will compute the ratio of total persons tested and vaccinated/total persons attending syringe exchange who were offered testing or vaccination to assess testing and vaccination program reach. We will use data collected during testing and vaccination intake, "Testing Intake Form", processed by our study team's data scientist which includes name, date of birth, and contact information. We will collect test results from the UO COVID-19 MAP laboratory. Following testing and vaccination, HIVA SSP clients will have the opportunity to take a follow-up survey, "Aim 1 Post-Testing Survey". At the time of testing or vaccination, the HIVA testing facilitator will invite clients to complete the testing intake and obtain informed consent and authorization for sharing protected health information. Consent, information sharing authorization, and the testing intake and consent will be completed electronically. The "Aim 1 Post-Testing Survey" will be collected either electronically either on Qualtrics or through a secure data collection tool provided by the CDCC or via paper and pencil. Research assistants will administer the "Aim 1 Post-Testing Survey".

Aim 1, Step 1 (Testing or vaccination Facilitator, Consent and HIPAA Authorization): Participate in testing or vaccination and receive \$10 to get tested or vaccinated and share testing information.

Aim 1, Step 2 (Research Assistant, no additional consent): Participate in "Aim 1 Post-Testing Survey" and get \$20 for completing the 20-min survey.

Data from steps 1 and 2 will be shared with the RADx-UP CDCC as required by our funder. The information that will be shared is summarized in the consent form.

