All individuals who participate in Aim 2 will be invited to complete an additional longer survey (i.e., "Post-Testing Survey"; 20 minutes) that includes common data element (CDE) questions. This survey will be completed during a future visit to syringe exchange or via e-mail, phone, text, or Facebook.

The target sample size for the RCT in Aim 2 is 350 unique individuals. The RCT will be initiated once IRB approval is received and we anticipate it will take approximately 3-4 months to reach the target sample size. Aim 2 data will be shared with the RADx-UP CDCC as required by our funder. The information that will be shared is summarized in the consent form. We plan to enroll 350 participants.

Data Analysis: We will use a randomized control trial to evaluate whether Connect2Test + Contingency Management increases COVID-19 testing utilization in comparison to contingency management alone. We will also test whether SDOH and key motivational variables (collected via Aim 2 Brief Client Survey) moderate intervention effects. We will use chi-square tests to examine whether the expected rates of testing utilization vary by condition. We will use logistic regression to examine whether SDOHs moderate intervention effects.

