Study Population: The study population will be people who inject drugs (PWID) and use HIVA's SSP services in Oregon. We anticipate the sample characteristics to be comparable to demographics for individuals who typically participate in syringe exchange. Specifically, we expect 6% Hispanic and 94% non-Hispanic, with 85% of individuals identifying as White in both ethnic groups and the remaining 15% identifying as African American, Asian, Pacific Islander, American Indian/Alaska Native, or more than one race. Only individuals 18 and older will be eligible to participate in testing, vaccination, and the intervention study. All study and intervention materials will be available in English. Although all participants regardless of language spoken will be invited to test and vaccinate; only participants who speak English will be eligible for the RCT (Aim 2), as Connect2Test materials will only be available in English. For Phase II, We anticipate approximately 3800 unique participants will be included in Aim 1 and approximately 350 unique participants will be included in Aim 2. All HIVA SSP clients (up to testing capacity, i.e., 150 per week) will have access to and be invited to test. We expect an excess of male participants (i.e., 60%), based on the demographics of persons who use syringe exchange services. Across all sites, we expect to offer testing to 3800 unique individuals in Year One and to administer approximately 150 tests per week. For Phase II, Aim 2, we anticipate recruiting up to 20 HIVA staff and volunteers to participate in the training sessions and MI pre-post survey.

Recruitment Procedures:

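### Vaccination is modelled on randomised condition alone: adding vaccination status recorded before randomisation, with all randomised clients kept, would be a cheap gain in precision and interpretation (minor; not a bias)

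*SAP*

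**What the plan says.** Phase II Aim 2b of the protocol (Specific Aims) sets the trial to compare contingency management alone with contingency management plus Connect2Test "on SARS-CoV-2 testing and COVID-19 vaccination uptake". The Data Analysis paragraph for Phase II Aim 2 then covers testing only: whether the combination "increases COVID-19 testing utilization in comparison to contingency management alone". The SAP therefore holds the only vaccination model. It is to "compare rates of COVID-19 testing and vaccination administered on the same day of the intervention and anytime during the 9-month follow-up period", with a null model followed by "the full model that included the study randomized condition as the predictor". Site is the upper level of the model, and no baseline covariate is named. The SAP also lists "tests of baseline equivalency of randomized groups", without naming the variables or saying that the results feed into the model.

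Under Study Population, the trial requires age 18 or over and English; vaccination status is not a criterion. On repeat use of testing and vaccination, Overall Study Design says "Some of these individuals will be repeat testers and vaccinators". Recruitment Procedures adds that vaccination is offered at every visit.

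The Intervention testing paragraph places the Aim 2 Brief Client Survey before randomisation; its items are not reproduced. Recruitment Procedures repeats the same survey about 3 weeks after enrolment.

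**The concern.** A client who is not due a dose has little chance of being vaccinated that day, whichever arm they are in. Status at entry is therefore likely to predict the vaccination outcome, most of all in the same-day window. Leaving it out costs two things.

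- **Precision.** Part of the outcome variation could be explained by one or two baseline items and is not.
- **Interpretation.** The plan does not report how many clients were due at entry. A small same-day difference could mean a weak intervention, or a sample with few clients in a position to be vaccinated.

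Testing for baseline balance supplies neither, because it does not change the model.

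**Working it through.** **Inputs.** The only design figure is the target of 350 (protocol, Phase II Aim 2). It comes with no alpha, power, rates or effect size, so it cannot be reproduced. Assumed here: 1:1 allocation (175 per arm), two-sided 5%, and 30-60% of clients due at entry. All uptake rates below are also assumptions.

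**Why the gain depends on uptake.** Let d be the share due, p the mean uptake among those due, δ the arm difference among those due, n = 175, and suppose no events occur in the rest.

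- Unadjusted: z = dδ / √[2·dp(1−dp)/n]
- Stratified by status: z = δ / √[2·p(1−p)/(nd)]
- Ratio, stratified to unadjusted: √[(1−dp)/(1−p)]

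With d = 0.40 and power ≈ Φ(z − 1.96):

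- 10 v 20% if due (p = 0.15): unadjusted z = 0.04/0.0254 = 1.575, power 35%. Ratio √(0.94/0.85) = 1.052, so z = 1.657, power 38%.
- 30 v 50% if due (p = 0.40): unadjusted z = 0.08/0.0392 = 2.041, power 53%. Ratio √(0.84/0.60) = 1.183, so z = 2.415, power 68%.

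The ratio approaches 1 as p falls, so low uptake leaves little to gain.

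**Simulation** (20,000 trials per scenario; score test, unadjusted v stratified by status). Power, %:

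| Window | Uptake if due / otherwise | Due | Unadjusted | Exact status | 15% misreported |
|---|---|---|---|---|---|
| Same day | 10 v 20% / none | 40% | 34.6 | 37.8 | 36.2 |
| Same day | 20 v 35% / none | 40% | 43.6 | 51.3 | 47.3 |
| Same day | 30 v 50% / none | 40% | 53.7 | 67.8 | 60.3 |
| Same day | 5 v 12.5% / none | 30% | 24.4 | 26.8 | 26.1 |
| Nine months | 20 v 35% / 2 v 4% | 50% | 60.7 | 65.7 | 63.2 |
| Nine months | 20 v 35% / 10 v 20% | 50% | 82.2 | 83.1 | 82.6 |

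- Same day, 12 scenarios: gain of 2.7 to 14.1 points with exact status (median 7.3). With 15% misreported it is 1.0 to 6.5 (median 2.9), a loss of 1 − 2.9/7.3 = 60% of the median gain.
- Same day, uncommon uptake (5 v 12.5% if due): gain of 1.4 to 2.4 points exact, 0.6 to 1.7 with 15% misreported.
- Nine months, 36 scenarios: −0.3 to 11.2 points exact (median 2.4), −0.3 to 4.8 with 15% misreported. Losses, never above 0.5 point, arise only where status barely predicts vaccination.
- A separate set at a conditional odds ratio of 2.5 gave 0-4 points at 5-10% control uptake among clients unvaccinated at entry, and 4-22 points at 40%.

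**With the site level.** Nine sites, random intercept, assumed site SD 0.5, weak penalty on the status term; same day, 40% due. Power unadjusted / exact / 15% misreported was 31.8 / 36.8 / 33.8% at 10 v 20% and 51.1 / 66.0 / 57.1% at 30 v 50%. The median odds ratio moved from 2.08 to 2.29 and from 1.83 to 2.38: the adjusted one is conditional on status.

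**No bias.** Under the null, size was 4.4-5.2% for the score tests and 3.7-5.6% for the site-level models, adjusted or not.

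**Reading a result.** For 8 v 14% among all randomised, OR = (0.14/0.86)/(0.08/0.92) = 1.87, 95% CI 0.94 to 3.74. If events occur only among those due, the 6-point difference is 6/0.6 = 10 points when 60% were due, 6/0.4 = 15 at 40%, and 6/0.3 = 20 at 30%.

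**Chance imbalance.** The SD of the arm difference in share due is √[2d(1−d)/175] = 4.9 to 5.3 points. The arms would differ by 5 points or more in 31-35% of trials and by 10 or more in 4-6%.

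**The case against.** The strongest reply is that this is optional covariate adjustment of an analysis that is already valid. Several parts of that reply stand.

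- **Prognostic strength is assumed.** A reader might infer that status is a documented, strong predictor. The documents give no link between status and uptake. Clients with no vaccination are the ones interviewed about delay or refusal, while vaccinated clients may return for another dose. The same-day scenarios, with no events among those not due, favour adjustment most.
- **Uptake may be low.** Overall Study Design plans 1,200 vaccinations against 15,600 tests, 1 to 13. That is not a per-visit rate, but it sits more easily with the small gains.
- **The same-day model may not fit as written.** If no client recorded as not due is vaccinated, the status coefficient has no finite estimate. Switching to a Mantel-Haenszel analysis at that point would drop the site level and be chosen after seeing the data.
- **Status may already be collected.** The survey items are not shown, and the SAP does not name its baseline variables, so absence cannot be claimed.

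A reader might also infer that every other source of status comes after randomisation and must be barred. The protocol does not support that. Aim 1 is described as ongoing from Phase I, and Table 2 keeps the Aim 1 vaccination intake of consenting clients to link data over time. A client could also have completed the testing-table survey before joining the trial. What matters is the date of the record, not its source.

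The reply does not remove the interpretation gap. Even where the power gain is negligible, a same-day result without the number due is hard to read.

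**Conclusion.** A minor point that holds: a cheap improvement in precision and interpretation. The vaccination model omits entry status, and nothing in eligibility makes status uniform. The expected gain is about 0-4 points of power when uptake is low or status predicts weakly, and up to about 14 points same day with exact status and high uptake. These figures rest on 175 per arm, 30-60% due and assumed uptake rates, none of them documented.

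A reader might conclude that the unadjusted comparison is biased, or that clients not due should be excluded. Neither follows. Randomisation protects the comparison, and the simulated size is close to 5%. Analysing only the reported-due subset, against all randomised unadjusted, changed power by −4.5 to +1.8 points same day and by −41 to −3 at nine months with 15% misreporting. That subset is supportive at most.

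**What to change.** 1. Confirm that COVID-19 vaccination status (doses and date of last dose) is in the enrolment copy of the Aim 2 Brief Client Survey, or add it while enrolment is open. Any record dated before randomisation may supply it, including earlier Aim 1 intake or survey records linked by ID where consent allows. Records dated after randomisation, including the 3-week repeat of the survey, may not.
2. Keep all randomised clients and add status to the site-level model in both windows, with 'not reported' as a category. Name in advance one method that stays finite if no client recorded as not due is vaccinated, for example a penalised status term in the site-level model. State that the adjusted odds ratio is conditional, and show the unadjusted one beside it.
3. Report by arm the number due at entry under the vaccination programme's own rule, cited in the SAP, with that subset's result as supportive only.
4. The SAP is written in the past tense. If the analysis has been run, keep the unadjusted result primary and label the adjusted one post hoc. If no status dated before randomisation exists, state the dilution as a limitation.

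**Cost.** SAP wording if status is already held, one or two survey items if it is not and enrolment is open, or one limitation sentence if it was never recorded. The downsides are error in self-reported status and an adjusted odds ratio that is not directly comparable with the unadjusted one.
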